9.6 Data Management

The study will be conducted by IQVIA in collaboration with research partners. The processes for database management differ by data source.

Overall, routine procedures or practice will include maintaining security and data confidentiality, following statistical analysis plans, and performing quality-control checks of analysis programs. Data extracts and analysis programs will be stored to allow any necessary future analysis.

In Germany and in Spain, data management and analysis will be performed by the respective research partner (Team Gesundheit and SIDAP) according to their respective routine procedures. IQVIA will receive filled-in result tables from these external vendors. No analytical data sets will be transferred to IQVIA.

In Sweden, IQVIA will receive study specific data sets from the National Board of Health and Welfare (NBHW) generated according to routine processes at the data holder and a study-specific data application form for data extraction. The analysis will be done by data source experts at IQVIA. Storage of analytical data sets and programs will be handled by IQVIA.

In France, data will directly be extracted and stored by the CNAM (national health insurance). IQVIA has access to the study dataset via a secured portal. At IQVIA analysis will be done by data source trained statisticians. Storage of analytical programs will be handled by IQVIA.

At IQVIA, the DUS will be conducted according to the Standard Operating Procedures (SOPs) of IQVIA's Real World & Analytics Solutions.

This study will follow relevant chapters of European Network of Centres for Pharmacoepidemiology and Pharmacovigilance (ENCePP) and International Council for Harmonisation of Technical Requirements for Pharmaceuticals for Human Use (ICH) guidelines for data management.

9.7 Data Analyses

The data analyses will be described and further detailed in the Statistical Analysis Plan (SAP). The described analyses below might be revised, and adjustments might occur as needed.

9.7.1 General Considerations

Given the study objectives the analyses will be mainly descriptive and will be conducted by country, by active substance and study time periods (both pre-implementation periods and post-implementation period). To allow for analysis across all data sources used in the study, a meta-analytic approach will be used to assess and pool the results from the four study countries together for each active substance (see 9.7.3.4).

The analyses will be provided for the overall class of oral retinoids and for the single active substances. Categorical variables will be presented as counts (n), proportions (%) with CI where relevant as for parameters used to address the primary objective and for the comparison of the incidence of exposed pregnancies. Continuous variables will be presented as means with standard deviation (SD) and as medians with interquartile range (IQR), where appropriate.

Changes in the reimbursement policy for contraceptives in the healthcare systems of the study countries will be considered to discard any differential misclassification of exposure.

The statistical unit will be the oral retinoid treatment episode and patient as well as prescription where appropriate. Patients who have multiple treatment episodes of oral retinoid use will be entered the cohort for analysis more than once.

The term “use” in the context of the analysis refers to the prescription or dispensing of drugs or IUD.

In the analysis, prescriptions of patients will be followed from the exposure start date to censoring date, i.e., transfer out of the database incl. death or the end of the study period, whichever comes first.

Statistical analyses will follow the tables shells validated by the MAH consortium and will be displayed using tables, listings and/or graphs. The statistical analysis will be conducted using SAS or an equivalent statistical analysis software. A detailed statistical analysis plan (SAP) will be prepared prior to data extraction.

The statistical results of all target countries and all active substances will be presented in a single report.

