8. RESEARCH QUESTION AND OBJECTIVES

The aim of the DUS is to address the following research question: Is there a difference in physicians' prescribing and monitoring practice in the periods before and after the update of the pregnancy prevention programme (PPP) for the oral retinoids acitretin, alitretinoin, and isotretinoin when treating women of childbearing potential?

The objectives of the DUS are:

Primary objective:

To evaluate the changes in the prescribing and monitoring practices following the update of the PPP in females of childbearing potential receiving prescriptions of the oral retinoids acitretin, alitretinoin, or isotretinoin by comparing the following key elements of the PPP between the pre- and the post-implementation period:

- Contraceptives* before, during, and after treatment with oral retinoids
- Time interval between prescription dates for oral retinoids during treatment episode
- Laboratory pregnancy tests – where available - before, during, and after treatment with oral retinoids

* contraceptive methods that require prescription and which are, therefore, captured in the administrative databases

Secondary objectives:

- To describe the patient profile during the pre-and the post-implementation period, with respect to:
 - Patient age
 - Indication for oral retinoids
- To describe the prescriber specialty during the pre-and the post-implementation period
- To describe the exposure characteristics during the pre-and the post-implementation period, with respect to:
 - Active substance
 - Dose
 - Treatment duration
- To describe the incidence of pregnancies exposed to oral retinoids during the pre-and the post-implementation period
- To stratify the key elements of the PPP described in the primary objective by oral retinoid substance
- To describe trends in the physician's prescribing and monitoring practice of oral retinoids with respect to measures of the PPP (contraceptive use and performance of pregnancy tests) over the entire duration the study

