9. RESEARCH METHODS

9.1 Study Design

This is a multicounty, multisource, observational cohort study in females of childbearing potential receiving oral retinoids (i.e., acitretin, alitretinoin and isotretinoin) using established data sources in different European countries (i.e., France, Germany, Spain, and Sweden)

The study will employ a pre-post design to evaluate the effectiveness of the implementation of the updated RMMs with respect to the PPP according to the following schedule:

- Pre-implementation period: period prior to the date of the implementation of the updated RMMs
- Post-implementation period: period after the implementation of the updated RMMs

Periods will be defined as (also see Figure 1):

Pre-implementation period: The period before the implementation of the updated RMMs. The RMM tools will be distributed in the fourth quarter 2018 (the exact date may vary depending on the country). The pre-implementation period captures two periods:

- Pre-referral: the 2-year period before referral start in July 2016. This period will be used for the before and after comparison with the post-implementation period.
- Post-referral: the 2.5-year period between the referral start date in July 2016 and the distribution of the RMM tools in the target countries (assumed until December 2018). The duration of this period may vary depending on the duration of the approval and the distribution of the RMM tools in each country.

Post-implementation period: This period captures the time starting after the distribution of EM until December 2020. The start date of the period in each country will depend on the date on which the EM is approved by the respective national competent authorities.

The final dates of the study periods depend on the final schedule of the implementation of the updated RMMs in each country.

Figure 1: Overview of study periods

A single database for all target countries is not available. Therefore, a study approach was chosen which includes multiple data sources to gather drug utilisation data for oral retinoids (acitretin, alitretinoin and isotretinoin) in the European countries of interest.

Databases with longitudinal secondary patient data collected continuously over time will be used preferably to provide the most comprehensive data for the outcomes of interest.

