9.7.2 Main analyses

The main analysis will cover the prescribing and monitoring patterns of oral retinoids during the pre- and post- implementation periods in females of childbearing age (13-49 years of age, inclusive) to meet the primary study objective. The analysis will be descriptive in nature. The first oral retinoid prescription of a treatment episode will be considered as exposure start date for the analyses of treatment episodes.

Measures related to the PPP

The following analyses will be performed:

- Laboratory pregnancy tests
 - Percentage of patients with laboratory pregnancy test performed at treatment start (up to 7 days before exposure start date)
 - Percentage of patients with laboratory pregnancy tests performed during treatment
 - Percentage of patients with laboratory pregnancy tests performed monthly according to the SmPC during treatment
 - Frequency of laboratory pregnancy tests during treatment, by month of treatment
 - Percentage of patients with laboratory pregnancy tests performed after treatment stop
 - For all retinoids: percentage of patients with laboratory pregnancy test performed within two months after treatment stop
 - For acitretin: performance of laboratory pregnancy tests beyond 1 month up to 3 years after treatment stop (depending on the length of individual follow-up of patients)
- Contraceptives

- Percentage of patients with prescription of hormonal contraceptives before treatment start (up to 3 months before the exposure start date or longer depending on the type of contraceptive)
- Percentage of patients with use of IUDs before treatment start (up to 5 years before exposure start date)
- Percentage of patients with concomitant use of contraceptives (hormonal contraceptives and / or IUD) during treatment
- Percentage of patients with use of contraceptives (hormonal contraceptives and / or IUD) within two months after treatment stop
- For acitretin: percentage of patients with use of contraceptives (hormonal contraceptives and / or IUD) beyond 1 month up to 3 years after treatment stop (depending on the length of individual follow-up of patients)
- Periodicity of oral retinoid prescriptions
 - Time interval between prescription dates for oral retinoid prescriptions during treatment (in days)
 - Proportion of oral retinoid users with monthly prescription intervals during treatment

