3.2 Does the protocol specify whether the study is based on primary, secondary or combined data collection?				9.1
3.3 Does the protocol specify measures of occurrence? (e.g. incidence rate, absolute risk)				9.3
3.4 Does the protocol specify measure(s) of association? (e.g. relative risk, odds ratio, excess risk, incidence rate ratio, hazard ratio, number needed to harm (NNH) per year)				
3.5 Does the protocol describe the approach for the collection and reporting of adverse events/adverse reactions? (e.g. adverse events that will not be collected in case of primary data collection)				11

Comments:

--

Section 4: Source and study populations	Yes	No	N/A	Section Number
4.1 Is the source population described?				9.4

Section 4: Source and study populations	Yes	No	N/A	Section Number
4.2 Is the planned study population defined in terms of:				
4.2.1 Study time period?				9.2.1
4.2.2 Age and sex?				9.2.1
4.2.3 Country of origin?				9.2
4.2.4 Disease/indication?				
4.2.5 Duration of follow-up?				9.7.2
4.3 Does the protocol define how the study population will be sampled from the source population? (e.g. event or inclusion/exclusion criteria)				9.2

Comments:

This is a database study with focus of the study is on the prescribing patterns of physicians, patients will be follow-up over the individual treatment episodes and available follow-up time in the database, if applicable

Section 5: Exposure definition and measurement	Yes	No	N/A	Section Number

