9.3.2 Outcomes? (e.g. International Classification of Diseases (ICD)-10, Medical Dictionary for Regulatory Activities (MedDRA))				9.4
9.3.3 Covariates?				9.4
9.4 Is a linkage method between data sources described? (e.g. based on a unique identifier or other)				9.4.1

Comments: Linkage will only apply to registry data in Sweden

--

Section 10: Analysis plan	Yes	No	N/A	Section Number
10.1 Is the choice of statistical techniques described?				9.7.1
10.2 Are descriptive analyses included?				9.7.1
10.3 Are stratified analyses included?				9.7.1
10.4 Does the plan describe methods for adjusting for confounding?				
10.5 Does the plan describe methods for handling missing data?				9.7.6
10.6 Is sample size and/or statistical power estimated?				9.5.1

Comments:

--

Section 11: Data management and quality control	Yes	No	N/A	Section Number
11.1 Does the protocol provide information on data storage? (e.g. software and IT environment, database maintenance and anti-fraud protection, archiving)				9.6
11.2 Are methods of quality assurance described?				9.8
11.3 Is there a system in place for independent review of study results?				9.8

Comments:

--

Section 12: Limitations	Yes	No	N/A	Section Number
12.1 Does the protocol discuss the impact on the study results of:				
12.1.1 Selection bias?				9.9

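### The primary before–after comparison has no defined measure of change with an interval and no adjustment for age

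*Protocol*

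**What the plan says.** - **Objective.** Section 8 sets out to evaluate changes by "comparing the following key elements of the PPP between the pre- and the post-implementation period". Section 9.1 names the reference, the two-year pre-referral phase: "This period will be used for the before and after comparison with the post-implementation period".
- **Main analysis.** Section 9.7.2 lists percentages by period and states: "The analysis will be descriptive in nature". Section 9.7.1 offers "proportions (%) with CI where relevant as for parameters used to address the primary objective", and means with SD or medians with IQR for continuous variables. No contrast between periods is defined.
- **Unit.** Section 9.7.1 names episode, patient and prescription as possible units and adds: "Patients who have multiple treatment episodes of oral retinoid use will be entered the cohort for analysis more than once". Section 9.7.2 words most outcomes per patient, and the time-series outcomes in 9.7.3.5 are per episode.
- **Annex 2 checklist.** Item 3.4, "Does the protocol specify measure(s) of association", is ticked N/A. Item 10.4, "Does the plan describe methods for adjusting for confounding", is ticked No. Item 7.1 (how confounding is addressed) is N/A, and item 12.1.3 (residual confounding) is No.
- **Age.** Section 9.7.3.1 describes age as a secondary item in bands 13–20, 21–35 and 36–49.
- **German contraceptive records.** Section 9.4.1.2 ties reimbursement to age, with the limit raised from 20 to 22 on 29 March 2019, inside the post-implementation period. Section 9.7.1 promises to consider reimbursement changes but gives no method.

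**The concern.** The study will be read as a verdict on whether practice changed. A reader given two percentages with two separate intervals has no stated estimate of that change and no statement of its precision.

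The two cohorts are centred 4.5 years apart (July 2015 and January 2020). If the age mix of retinoid users differs between them, the crude percentage with a contraceptive record will differ too, even if every prescriber behaves as before. Such a shift could be taken for an effect of the updated programme, or could hide one.

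Timing adds to this. Under section 9.6 the German and Spanish partners return completed result tables and no analytical data sets. An age-standardised change that is not requested before extraction cannot be derived centrally afterwards.

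**Working it through.** **1. The plan's own precision figure.** Section 9.5.1 uses n = 1.96² p(1−p)/e² for one proportion. At p = 50% and e = 5 points: 3.8416 × 0.25 / 0.0025 = 384.2, so 385. At p = 20%: 3.8416 × 0.16 / 0.0025 = 245.9, so 246. Both agree with Table 4.

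**2. What that gives for the change.** The half-width of a difference between two independent periods of n each is 1.96 √(2p(1−p)/n).
- 385 per period, p = 50%: 1.96 √(0.5/385) = 7.1 points.
- 246 per period, p = 20%: 1.96 √(0.32/246) = 7.1 points.
- For ±5 points on the change: 2 × 384.16 = 768.3, so 769 per period at p = 50%, and 2 × 245.86 = 491.7, so 492 at p = 20%.

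Table 4 is right for what it sizes, but that is one period's percentage and not the comparison.

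**3. German precision for the change.** The three-year feasibility count is 3,729 women. Assume two thirds of it per two-year period: 2,486. At p = 16%: 1.96 √(2 × 0.16 × 0.84 / 2,486) = 2.0 points.

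**4. Effect of an age shift alone, Germany.** Inputs from section 9.4.1.2: 16% of retinoid users with a contraceptive record, and 2% of women above 20. Assumption: young users make up a share s of 20% to 50%. The rate in young users is then (0.16 − 0.02(1−s))/s, and its gap to the older rate is 0.14/s.

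| s | rate in young | gap | effect of a 5-point rise in s |
|---|---|---|---|
| 20% | 72% | 70 points | 0.05 × 70 = 3.5 points |
| 30% | 48.7% | 46.7 points | 2.3 points |
| 40% | 37% | 35 points | 1.75 points |
| 50% | 30% | 28 points | 0.05 × 28 = 1.4 points |

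The shift in young share that equals the 2.0-point half-width runs from 2.0/70 = 2.9 points (s = 20%) to 2.0/28 = 7.1 points (s = 50%).

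**5. Repeat episodes, if they are the unit and are treated as independent.** Design effect 1 + (m−1)ρ, with assumed m = 1.1 to 1.5 episodes per woman and ρ = 0.3 to 0.8. This runs from 1 + 0.1 × 0.3 = 1.03 to 1 + 0.5 × 0.8 = 1.40. Intervals should then be √1.03 = 1.015 to √1.40 = 1.18 times as wide.

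**6. Where a contrast would be thin.** With the same two-thirds rule and p = 50%, the half-width of the change for acitretin is 13.7 points in Germany (153 × 2/3 = 102 women) and 10.1 in Spain (281 × 2/3 = 187).

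**The case against.** The strongest defence is that the study is declared descriptive, that no hypothesis is claimed (checklist item 2.1.4 is N/A), and that details go to a SAP not shown here. This carries weight for the variance method, which a SAP commonly settles. It does not cover the effect measure or the adjustment: the protocol answers both itself, as N/A and No, although its primary objective is a comparison. A descriptive study can still put an interval on a difference.

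A second defence is the segmented regression in section 9.7.3.5, which would give level and slope changes with standard errors. It is secondary and runs only with at least 6 time points per period and 100 observations per point. Its parameters are finally chosen after the primary results are known. Its model holds time, period and their product, with no age term, and prescription intervals are not among its listed parameters.

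A third is that age is tabulated by period, so a shift would be seen. It would be seen, but the change would not be corrected for it.

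Several stronger readings are tempting but lack support:
- *The intervals are wrong because women re-enter.* The protocol does not say that independence will be assumed. The widening in step 5 is a possibility and is modest. For time between prescriptions, the plan names means and medians and no interval, so there is no interval to widen. A woman present in both periods would, with positive correlation, reduce the variance of the difference, so ignoring her overlap is conservative.
- *Change will be judged by whether intervals overlap.* No section adopts that rule.
- *Substance mix distorts the results.* Results and pooling are per substance, so only the overall-class figure is exposed. Isotretinoin makes up 3,492/3,729 = 93.6% of patients in Germany, 4,546/4,842 = 93.9% in Spain and 20,138/20,580 = 97.9% in Sweden.
- *Indication and specialty should be adjusted for everywhere.* In France specialty is not captured, and sections 9.3.2 and 9.9.2 leave no usable outpatient indication.

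**Conclusion.** The point holds for the primary comparison. It has no named measure of change with an interval and no age adjustment, and its unit is not fixed per outcome. This is a choice written into the protocol and should be changed.

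The size is illustrative. In Germany a 5-point age shift is worth about 1.4 to 3.5 points, roughly 0.7 to 1.75 times the 2.0-point half-width of the change. This rests on an assumed 20% to 50% share of young users, on two thirds of the three-year count per period, and on applying the 2% for women above 20 to older retinoid users, which may be a different group. A higher rate in older users would shrink the effect in proportion. The documents do not show that an age shift has occurred, and the age dependence is documented for Germany and not for the other three countries.

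**What to change.** In section 9.7.2:
- For each country, substance and primary proportion, report the pre-referral to post-implementation difference with 95% CI, standardised to the pre-referral age distribution. For the overall-class figure, standardise over substance as well.
- For German contraceptive outcomes, use age bands that separate the under-20, 20–22 and older groups; the planned 13–20 and 21–35 bands do not. Show the differences by band, because standardisation alone does not remove the March 2019 reimbursement change but separate bands make it visible.
- Fix one unit per outcome. Where it is the episode, cluster standard errors on the woman.
- Keep the crude percentages as description.

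In section 9.7.3.4, pool the within-country changes, not the period percentages. Recorded contraception runs from 7% of insured women aged 13–49 in Germany to an expected figure above 50% of women of childbearing age in France. Differences within country take out such constant gaps in level.

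Annex 2 items 3.4, 7.1 and 10.4 should be updated to match.

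The cost is some extra programming at each data partner, requested before extraction; age and substance are already extracted. Cells for alitretinoin (100 women in Germany, 15 in Spain) and acitretin will be sparse, and there the crude difference with its interval may have to stand.

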9.2.2 Exclusion Criteria

All females in the age group 13 to 49 years with available information that they are not of childbearing potential before initiation of oral retinoids (such as records of hysterectomy or sterilisation) will be excluded.

Data for the oral retinoids acitretin, alitretinoin, and isotretinoin will only be extracted from databases in target countries where the respective active substance has been granted market authorisation.

No further exclusion criteria will be applied.

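### After-treatment windows do not end when a new retinoid course starts, so the long acitretin measures count a later course's tests and contraception as after-treatment practice

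*Protocol*

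**What the plan says.** Protocol 9.7.1 follows patients from the exposure start date to a censoring date, which it defines as "transfer out of the database incl. death or the end of the study period, whichever comes first". The same section adds: "Patients who have multiple treatment episodes of oral retinoid use will be entered the cohort for analysis more than once".

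Protocol 9.7.2 sets these after-treatment measures:

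- Tests, all retinoids: "percentage of patients with laboratory pregnancy test performed within two months after treatment stop".
- Tests, acitretin: "performance of laboratory pregnancy tests beyond 1 month up to 3 years after treatment stop (depending on the length of individual follow-up of patients").
- Contraception, all retinoids: "Percentage of patients with use of contraceptives (hormonal contraceptives and / or IUD) within two months after treatment stop".
- Contraception, acitretin: the percentage with use "beyond 1 month up to 3 years after treatment stop (depending on the length of individual follow-up of patients").

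The at-start measure of any episode is: "Percentage of patients with laboratory pregnancy test performed at treatment start (up to 7 days before exposure start date").

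To be analysed after treatment, a woman needs at least 2 months of follow-up beyond the episode (end of 9.7.2). Nothing is said about a restart. Treatment stop is the last prescription date plus its days' supply, and the gap that separates two episodes is left to the SAP (9.7.3.2). Section 9.2.2 excludes women known to be "not of childbearing potential before initiation of oral retinoids" and applies no further exclusions.

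**The concern.** The after-treatment phase is one of the three phases (before, during, after) in which the primary objective compares testing and contraception. The listed censoring events do not include the start of a further course, yet the design expects women to have several.

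Take an acitretin user who stops, is off treatment for six months and then restarts. Her test before the restart, her tests during the second course and her contraception during it all lie between 1 month and 3 years after the first stop. As written they count towards after-treatment practice for the first course. The same records are also counted under the second course, where they belong.

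At stake is what the measure means. If the updated programme improved only what happens at or during a course, the after-treatment figure would rise too, with no change in practice after stopping.

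**Working it through.** **1. The plan's own figure.** The only size criterion is the precision target in 9.5.1: n = 1.96² × p(1−p) / e². With p = 0.5 and e = 0.05 this is 3.8416 × 0.25 / 0.0025 = 384.2, so 385, as stated. The concern does not depend on it; it serves only as a yardstick.

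**2. When a restart can fall inside a window.** Let g be the allowed gap in days from treatment stop to the next prescription. A new episode can start no earlier than day g + 1, and its 7-day at-start look-back reaches back to day g + 1 − 7 = g − 6. Two months is taken as 60 days.

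| Gap g | Earliest restart | Earliest at-start test | Effect on the two-month window |
|---|---|---|---|
| 30 | day 31 | day 24 | restart and its test can both fall inside |
| 60 | day 61 | day 54 | only the test (days 54–60) can fall inside |
| 67 | day 68 | day 61 | neither |

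An at-start test can enter while g − 6 ≤ 60, that is up to g = 66. Contraception during the new course can enter only while g + 1 ≤ 60, that is up to g = 59. The acitretin window of up to 3 years admits later courses at any gap shorter than the available follow-up.

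**3. How many women have the long window.** Acitretin users in Table 5 are 153/3,729 = 4.1% in Germany, 281/4,842 = 5.8% in Spain and 442/20,580 = 2.1% in Sweden. Together this is 876/29,151 = 3.0%. For France the table gives only boxes. Isotretinoin, at 93.6% to 97.9% of patients, has only the two-month window.

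**4. Illustration on assumed rates.** The documents give no restart, testing or after-treatment rates. Let p be the true share tested after stopping, r the share who restart inside the window, and q the share of restarters tested because of the restart. If these are independent,

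observed share = 1 − (1 − p)(1 − rq).

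For p = 20%, r = 10%, q = 50%: 1 − 0.80 × 0.95 = 24.0%. If only q rises between periods, from 50% to 80%, the false change is (1 − p) × r × 0.30.

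| r | Observed, q = 50% | Observed, q = 80% | False before-after change |
|---|---|---|---|
| 5% | 22.0% | 23.2% | 1.2 points |
| 10% | 24.0% | 26.4% | 2.4 points |
| 20% | 28.0% | 32.8% | 4.8 points |
| 30% | 32.0% | 39.2% | 7.2 points |

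For comparison, the plan's precision target is ±5 points.

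**The case against.** **This is SAP territory.** Section 9.7 leaves detail to the SAP, and 9.7.3.2 leaves the episode gap to it by name. An SAP could cut the windows correctly. That stands for the two-month measures, where the gap decides the matter. It is weaker for acitretin. There the window is limited only by individual follow-up, and the protocol's one definition of follow-up is the list in 9.7.1, which is stated and not deferred.

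**The 9.7.1 sentence describes follow-up in the database.** That follow-up has to run past a restart, or repeat episodes could not be found. This is fair. The missing element is a separate end for the after-treatment windows, not a change to database follow-up.

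**The affected group is small.** Acitretin is about 3% of counted patients outside France, and 9.9.2 already concedes that 3-year follow-up is unavailable for women treated after implementation. But 9.7.1 and 9.7.3.4 report and pool by active substance, so the larger isotretinoin group does not dilute an acitretin estimate.

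**A woman who has contraception is protected, whether or not she restarted.** True, so the contraceptive percentage is not false as a description of cover. It still does not show whether contraception continued because treatment had stopped, which is what the after phase is meant to show.

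**Two stronger readings are not supported.** A reader might infer that all after-treatment measures are contaminated. They are not necessarily: the windows are bounded, and a gap of about 67 days or more keeps restart tests out of the two-month window.

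A reader might also infer that a woman who conceives after stopping is wrongly scored, and that windows should end at conception. But conception without recorded contraception inside the required period is a genuine failure of the programme, and a test that detects it was performed. The fallback in 9.3.3, for sources with no timing information and no published method, dates pregnancy start at the first record minus 90 days. Any first record within 90 days of stopping would then put the estimated start at or before the stop date and erase the whole 60-day window.

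**Conclusion.** The point holds, mainly for the acitretin measures running beyond 1 month to 3 years. As written, they mix after-treatment practice with the at-start and on-treatment practice of later courses. For the two-month measures it holds only if the SAP's episode gap is shorter than about 67 days (taking two months as 60 days and the gap as running from the end of supply).

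The size is unknown. The false changes of 1.2 to 7.2 points rest entirely on assumed rates, and on restart practice improving while after-stop practice does not.

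Whether the effect cancels between periods is also open. If women treated before the referral are followed longer than those treated after implementation, their windows will hold more restarts. The documents do not settle this.

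**What to change.** In 9.7.1 and 9.7.2, and carried into the SAP:

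- End each after-treatment window at the earliest of the first prescription of a new oral retinoid episode, the censoring events already listed, or the end of the window.
- Do not count a test in the 7-day at-start look-back of the new episode as an after-treatment test of the preceding one.
- Report the percentages among women still retinoid-free, with the number whose window was cut by a restart, by period and country.
- A sterilisation or hysterectomy recorded after initiation may also end the window, in line with 9.2.2.
- Do not end windows at an estimated pregnancy start. Report after-treatment tests linked to a pregnancy record (for example Z32.1 in Annex 3.2) separately.

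The rule should be fixed before extraction. Under 9.6 the German and Spanish partners return completed tables only, so different handling could not be repaired centrally before pooling.

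The cost is wording and programming on dates already planned for extraction. The statistical price is somewhat fewer evaluable women, selected on not having restarted; the count of cut windows lets the reader judge how much that matters.
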